6.3.2 Lesion Reduction Category

The visible/clinical clearance of the target lesions will be rated according to the lesion reduction categories listed in Table 4. The lesion reduction category will be derived from the lesion size measurements at baseline and follow-up day 60 Post-NPS treatment described in **Section 6.3.1**. The % reduction will be calculated as the change in lesion size divided by the baseline value. This percentage will be categorized according to the table 4 below:

Table 4. BCC Lesion Reduction Categories

BCC Lesion Reduction Categories			
CLEAR 0mm/100% reduction	MOSTLY CLEAR 99-51% reduction	PARTIALLY CLEAR 50-25% reduction	NOT CLEAR <25% reduction

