3.0 PROTOCOL

3.1 Study Objectives

The primary objectives of this study are to evaluate the safety and effectiveness of the CellFX System in adults with low-risk basal cell carcinoma. Table 1 below reflects the study endpoints associated with the two objectives.

Table 1. Study Objectives and Endpoints

Objectives	Endpoints
Safety To evaluate the safety of the CellFX System in adults with low-risk basal cell carcinoma	Primary: 
 • No serious adverse events related to CellFX Treatment or Procedure Secondary: 
 • Local Skin Reactions (Investigator) • Procedural pain assessment (Subject)
Effectiveness To evaluate the effectiveness of the CellFX System in adults with low-risk basal cell carcinoma	Primary: 
 • Complete histological clearance of the target lesion on microscopic evaluation of hematoxylin and eosin stains Secondary: 
 • Visible/clinical clearance of the target lesion by clinical/dermatoscopic evaluation • Partial response of the study lesion as assessed by WHO criteria ($\geq 50\%$ decrease in the product of the longest perpendicular diameters of each target lesion) • SCAR-Q Appearance Scale (Subject) • Manchester Scar Scale (Investigator) • Healing assessment questions (Investigator)

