4.4 Schedule of Events and Evaluations

Schedule of events and evaluations required for this study are provided in **Table 3**.

Table 3. Schedule of Events

Study Activity/ Procedure	Visit 1 Screening/ Enrollment & Tx	Visits 2-4 3, 7, 14-days Post-Tx	Visits 5 30-days Post-Tx	Visit 6 Excision (60-days Post-Tx)	Visit 7 14-days Post Excision	Visit 8 30-days Post Excision	Visit 9 60-days Post Excision
Study Day	0	3/7/14	30	60	74	90	120
Visit Window	Day 0	±2 days	±5 days	±5 days	±3 days	±5 days	±5 days
Type of Visit							
OV – In-Office Visit Required OV/TM – In-Office Visit or Telemedicine Visit	OV	Visit 2 & 3: OV/TM Visit 4: OV	OV/TM	OV	OV	OV/TM	OV
Inclusion/Exclusion Informed Consent	✓						
Demographics, Medical HX, Fitzpatrick Skin Type, etc.	✓						
Lesion History	✓						
History of Pigmentary Changes	✓						
Photographs	✓ a	✓ * ✓ *	✓ * ✓ *	✓ a ✓ a	✓ a ✓	✓ * ✓ *	✓ ✓
Lesion Assessment (Investigator)	✓ a	✓ * ✓ *	✓ * ✓ *	✓ a ✓ a	✓ ✓	✓ * ✓ *	✓ ✓
Tattoo Treatment Area	✓						
CellFX Treatment	✓						
Procedural Pain Assessment (Subject)	✓			✓			
Surgical Excision				✓			
Suture Removal (as applicable)					✓		
SCAR-Q Appearance Scale (Subject)				✓ b ✓ b			✓ ✓
Manchester Scar Scale (Investigator)				✓ b ✓ b			✓ ✓
Healing Assessment Questions (Investigator)				✓ b ✓ b			✓ ✓
Lesion Measurement	✓			✓ b ✓ b			
Clinical Clearance Assessment				✓ b ✓ b			
Adverse Events	✓	✓ ✓	✓ ✓	✓ ✓	✓ ✓	✓ ✓	✓ ✓
Study Exit							✓

^a Pre- and post-procedure / Surgical Excision / Suture Removal

^b Pre-procedure / Surgical Excision

* Required for in-office visits only

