- All lesions will be examined and clinically assessed by the site investigator. If the visit is not performed in-office, clinical assessment is not required.
- A light bandage and/or any physician recommended dressing may be applied post-evaluation.
- Any adverse events will be identified and documented. If the visit is not performed in office, the clinical site must inquire regarding any adverse events either by phone call, text, e-mail or video conference.

4.8 14-Day Follow-up Visit (Visit 4)

- Photographic images of each study lesion will be taken.
- All lesions will be clinically assessed by the investigator.
- A light bandage and/or any physician recommended dressing may be applied post-evaluation.
- Any adverse events will be identified and documented.

4.9 30-Day Follow-up Visit (Visit 5)

- This visit may be performed in-office or as a telemedicine visit.
- Photographic images of each study lesion will be taken. Photographs are not required if the visit is not performed in-office.
- All lesions will be examined and clinically assessed by the site investigator. If the visit is not performed in-office, clinical assessment is not required.
- Any adverse events will be identified and documented. If the visit is not performed in office, the clinical site must inquire regarding any adverse events either by phone call, text, e-mail or video conference.

4.10 60-Day Follow-up Visit (BCC Surgical Excision Day – Visit 6)

- Photographic images of each study lesion will be taken.
- All lesions will be clinically assessed by the investigator.
- The site investigator shall assess each treatment area based on the Manchester Scar Scale

prior to excision.

- The site investigator shall complete the healing assessment questions for each treatment area prior to excision.
- Clinical measurements of the BCC lesion(s) shall be taken
- The site investigator shall complete the clinical lesion clearance assessment for each treatment area prior to excision.
- The subject shall assess each treatment area based on the SCAR-Q Appearance Scale prior to excision.
- A complete surgical tumor excision will be performed by the investigator with at least 5mm margins for each study lesion.
- The subject will be asked to rate his/her pain immediately after surgical excision by using a numerical rating score.
- All tissue shall be handled and shipped to the dermatopathology laboratory per the Tissue Handling and Analysis Procedure.

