APPENDIX B: Case Report Forms

Case Report Forms will be provided as a separate attachment.

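### Table 1 defines a clearance endpoint by clinical/dermatoscopic evaluation, but 6.3.2 derives it from caliper measurements alone; the two need reconciling, and Table 4 needs contiguous limits

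*Combined protocol and SAP*

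**What the plan says.** Section 3.1, Table 1, gives as a secondary effectiveness endpoint "Visible/clinical clearance of the target lesion by clinical/dermatoscopic evaluation".

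Table 3 (section 4.4) has one row for lesion measurement, marked at Visits 1 and 6, and another for "Clinical Clearance Assessment", marked at Visit 6 only, before excision. The Visit 6 list in section 4.10 keeps the two apart as well. One item reads "Clinical measurements of the BCC lesion(s) shall be taken"; another reads "The site investigator shall complete the clinical lesion clearance assessment for each treatment area prior to excision".

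Section 6.3.2 begins: "The visible/clinical clearance of the target lesions will be rated according to the lesion reduction categories listed in Table 4". It continues: "The lesion reduction category will be derived from the lesion size measurements at baseline and follow-up day 60 Post-NPS treatment". It refers to 6.3.1 for those measurements, where lesion size is the longest diameter multiplied by the longest perpendicular diameter, taken with calipers. The percent reduction from baseline is then placed in one of four Table 4 categories: CLEAR (0 mm, 100%), the category printed as "MOSTLY CLEAR 99-51% reduction", PARTIALLY CLEAR (50-25%) and NOT CLEAR (below 25%). No rounding rule is given.

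On the forms, Appendix B says: "Case Report Forms will be provided as a separate attachment".

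**The concern.** An investigator's clinical or dermatoscopic evaluation and a percentage computed from two caliper readings are different sources of information. Table 1 names the first. Section 6.3.2 uses the second under the same endpoint name, and does not say what part the scheduled Visit 6 assessment or dermatoscopy plays.

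What is at stake is the meaning of one reported result. Section 1.6 says the data will help design a pivotal study, so the report should be clear about whether its clearance rate is a clinical judgement or a size calculation. Settling this before the data are seen also avoids having two candidate clearance figures to choose between afterwards.

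A smaller matter is Table 4 itself. Its printed limits do not cover every attainable reduction, and one of the gaps lies next to CLEAR.

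**Working it through.** **Endpoint source.** The plan states no figure to reproduce here, so the check sets the passages side by side.

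| Place | What it provides | Dermatoscopy mentioned? |
|---|---|---|
| Table 1 (3.1) | Clearance by clinical/dermatoscopic evaluation | Yes |
| Table 3 (4.4) | Measurement row (Visits 1 and 6); clearance assessment row (Visit 6) | No |
| 4.10 | Measurement and investigator clearance assessment as separate items | No |
| 6.3.1 | Lesion size as a product of caliper diameters | No |
| 6.3.2 | Clearance category derived from the 6.3.1 sizes | No |

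The form's content is not given, so two cases are open.

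1. The Visit 6 form records an independent clinical judgement. Section 6.3.2 then reports a different measurement under the endpoint's name. Section 6 gives the judgement no analysis of its own beyond the general descriptive rule in 6.1.
2. The form records the Table 4 category. The assessment then has a use in 6.3.2, and what remains is that nothing in 4.10 or section 6 supports Table 1's reference to dermatoscopy.

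Table 1 and 6.3.2 do not agree in either case. Only the size of the mismatch differs.

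**Table 4 limits.** Inputs: the printed limits in 6.3.2, and the 1.5 cm lesion size limit in inclusion criterion 2 (4.2.1), read here as the longest diameter. The lesion dimensions are illustrative.

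Reduction = 1 - (Day 60 product / baseline product).

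| Baseline to Day 60 (mm) | Calculation | Reduction | Category as printed | After rounding to a whole percent |
|---|---|---|---|---|
| 9 x 9 to 8 x 5 | 1 - 40/81 | 50.62% | none | 51%, MOSTLY CLEAR |
| 12 x 10 to 1 x 1 | 1 - 1/120 | 99.17% | none | 99%, MOSTLY CLEAR |
| 15 x 15 to 1 x 1 | 1 - 1/225 | 99.56% | none | 100%, although a residual is measurable |

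Rounding therefore settles the first two. It fails from 99.5% to just below 100%. A 1 x 1 mm residual reaches 99.5% only if the baseline product is at least 1/0.005 = 200 mm². With whole-millimetre readings and a 15 mm limit, that means 15 x 14 (210) or 15 x 15 (225); 14 x 14 (196) and 15 x 13 (195) fall short. The awkward zone can be reached but is narrow.

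**The case against.** The strongest reply is that 6.3.2 already answers the question. It uses Table 1's endpoint name, says how clearance is rated, and gives the source of the rating. That stands. A reader might infer that the plan leaves it unknown which measurement will be reported; it does not, since 6.3.2 names the caliper measurements. The fault is that this source differs from the one in Table 1.

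Nor do the separate rows and list items prove that there is a separate instrument. A percent-change category needs measurements at Visits 1 and 6 and can only be completed at Visit 6, which is the pattern Table 3 shows. A reader might infer that an independent clinical judgement is collected and then ignored. Without the form, the documents do not establish that. They do not exclude it either: a form completed by the investigator sits awkwardly with a category that is derived by calculation.

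The slash in Table 1 may also mean that dermatoscopy is optional. Even so, no procedure or analysis says when it would be used or how it would count.

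On Table 4, ordinary rounding resolves most of the gaps, and the 0 mm condition suggests that a measurable residual is not CLEAR. Both points are fair. But no rounding rule is stated, and for 99.56% the rounded percentage and the 0 mm condition point to different categories.

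**Conclusion.** The point holds as a mismatch of definition. Followed as written, section 6 reports a size-derived category under the name of an endpoint that Table 1 defines by clinical/dermatoscopic evaluation. If the form merely records the Table 4 category, the mismatch shrinks to Table 1's dermatoscopic wording.

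The impact is minor. The endpoint is secondary, no hypothesis tests are planned (6.1, 6.3), and the primary endpoint, histological clearance, is unaffected. How often a clinical judgement and the caliper category would disagree cannot be computed from the documents. The Table 4 defect is real but should touch few lesions; the size given for it assumes whole-millimetre readings and the 1.5 cm limit as the longest diameter.

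A reader might extend the point to the precision of a clearance proportion when some subjects contribute two lesions, or to a missing comparison of clinical with histological clearance. Neither supports this finding. Section 6.3.2 states no interval, so precision is a separate matter. The plan does not promise the comparison, so leaving it out is not an error.

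**What to change.** Reconcile Table 1 and 6.3.2 according to what the Visit 6 form records.

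- If it records an independent investigator judgement, make that judgement the clearance endpoint, reported as the count and proportion of lesions. State whether and how dermatoscopy contributes, and keep the caliper categories as a separate summary.
- If it records only the derived category, amend Table 1 to say that clearance is derived from lesion measurements, and remove the dermatoscopic wording.

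In either case, define Table 4 on unrounded values:

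- CLEAR: 0 mm, 100% reduction
- MOSTLY CLEAR: more than 50% and less than 100%
- PARTIALLY CLEAR: 25% to 50% inclusive
- NOT CLEAR: less than 25%

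The cost is a few sentences in Table 1, 6.3.2 and Table 4. The assessment and the measurements are already scheduled, so no visit or procedure is added.

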6.3.3 Partial response of target (study) lesion as assessed by WHO criteria

Partial response will be assessed using the WHO criteria. Partial response is defined as a $\geq 50\%$ decrease in the product of the perpendicular diameters of each target/study BCC lesion compared to baseline. The 50% reduction will be determined through the product of the longest perpendicular bidimensional diameters (longest length and longest perpendicular width) of each study lesion treated. Calipers will be provided to each study site to perform the measurements per standardized procedures. A standard adhesive ruler will also be included in photographs taken of each study lesion. Partial response will be assessed for in-clinic measurements at follow-up day 60 Post-NPS treatment. The number and proportion of lesions meeting the definition of partial response and confidence interval for the proportion will be calculated.

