An initial NSR BCC feasibility study (NP-BC-005) demonstrated that the NPS Device was successful in treating basal cell carcinoma lesions without safety concerns. A portion of 1-2 biopsy confirmed BCC lesions were treated in the 48 Subjects enrolled. 48 NPS treated areas were evaluated by a board certified dermatopathologist. There was no presence of BCC located within the NPS treated area in all samples analyzed for superficial and nodular low risk BCC lesions. The treated areas showed favorable healing clinically.

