3.2 Study Design

This study is designed as a prospective, multicenter IDE feasibility study in up to 30 adult participants with low-risk basal cell carcinoma utilizing the CellFX System at up to 6 sites within the United States. The study will consist of a single treatment session with the CellFX System followed by surgical tumor excision (with 5 mm margins) 60 days post-treatment.

Eligible subjects with 1-2 histologically confirmed, primary BCC lesion(s) who meet the inclusion and exclusion criteria will be enrolled. The BCC lesion(s) may be present anywhere on the body except neck, axilla, hands, feet, or genitals. In cases where the subject has more than 1-2 BCC lesions that meet the study criteria, the PI will select the lesion(s) to include in the study.

The subject will receive treatment of their confirmed BCC lesion(s) with the CellFX system. The treatment area will be evaluated at 3-days, 7-days, 14-days, 30-days and 60-days post-NPS treatment. At the 60-day follow-up visit, participants will undergo complete surgical excision of the tumor plus 5 mm margins. The subject will return for 3 more follow-up visits post-excision at 14 days (suture removal), 30 days and 60 days (typical skin check post-surgical excision) for a total of 9 study visits. The 3-day, 7-day, and 30-day post-NPS treatment follow-up visits as well as the 30-day post-surgical excision visit may be performed as telemedicine visits.

The excised tissue at the 60-day post-treatment visit will be shipped for histological analysis. Preparation and analysis of the excised tissue will be performed by Pinkus Dermatopathology Laboratory and a board certified dermatopathologist who has extensive experience in interpreting cutaneous neoplasms. Details of the preparation, shipment and analysis of the excised tissue are provided in the Tissue Handling and Analysis Procedure.

Photography of the study lesion(s) will be captured along with the investigator's assessments at all in-office visits. Detailed instructions for photography of the lesion area are provided in the photography instruction manual.

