4.2.1 Inclusion Criteria

Candidates for this study must meet **ALL** the following criteria:

1. Subject is at least 22 and no older than 85 years of age.
2. Subject has 1-2 primary, non-recurrent, superficial, or nodular visible basal cell carcinoma lesion up to 1.5 cm in size with well-defined borders that has been verified by biopsy.
3. Lesion(s) is appropriate for full linear excision with 5 mm margins.
4. Subject is capable of giving signed informed consent, which includes compliance with the requirements and restrictions listed in the ICF and in this protocol.

5. Subject gives voluntary, written informed consent to participate in this clinical investigation and from whom consent has been obtained.
6. Subject is willing to have BCC lesion(s) treated in a single treatment session and must comply with all study procedures including follow-up visits.
7. Subject consents to have photographs taken of the BCC lesion(s).
8. Subject agrees to refrain from using all other lesion removal products or treatments (topical medication including over-the-counter medications or treatments from PI or another physician) during the study period.
9. Subject agrees to refrain from prolonged sun exposure of the treatment area during the study period.

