- Any adverse events will be identified and documented.

4.11 14-Day Post-Excision Follow-up Visit (Visit 7)

- Photographic images of each study area will be taken.
- Each study area will be clinically assessed by the investigator.
- Sutures shall be removed, as applicable.
- Photographic images of each study area will be taken post-suture removal.
- Any adverse events will be identified and documented.

4.12 30-Day Post-Excision Follow-up Visit (Visit 8)

- This visit may be performed in-office or may be performed as a telemedicine visit.
- Photographic images of each study area will be taken. Photographs are not required if the visit is not performed in-office.
- Each study area will be examined and clinically assessed by the site investigator. If the visit is not performed in-office, clinical assessment is not required.
- Any adverse events will be identified and documented. If the visit is not performed in office, the clinical site must inquire regarding any adverse events either by phone call, text, e-mail or video conference.

4.13 60-Day Post-Excision Follow-up Visit (Visit 9)

- Photographic images of each study area will be taken.
- Each study area will be clinically assessed by the site investigator.
- The site investigator shall assess each treatment area based on the Manchester Scar Scale.
- The site investigator shall complete the healing assessment questions for each treatment area.
- The subject shall assess each treatment area based on the SCAR-Q Appearance Scale.
- Any adverse events will be identified and documented.

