6.3.4 SCAR-Q Appearance Scale (Subject)

The SCAR-Q is a patient-reported outcome instrument designed to measure outcomes specific to any type of scar. This instrument has subscales for scar appearance, psychosocial impact and scar symptoms. Least-square means and confidence intervals will be calculated for each scale and subscale using generalized linear models with lesion size included as a fixed effect.

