6.3.5 Manchester Scar Scale (Investigator)

The Manchester Scar Scale evaluates the following five characteristics of scar: color (score: 1–4), distortion (score: 1–4), contour (score: 1–4), texture (score: 1–4), and transparency (score: 1–2). The distribution of responses will be summarized for each characteristic. Least-square means and confidence intervals will be calculated for the total score using generalized linear models with treatment lesion size included as a fixed effect.

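### Subjects may contribute two lesions, but the scar-score models (6.3.4, 6.3.5) and the lesion-level interval for partial response (6.3.3) make no allowance for it; the effect is small unless many subjects have two

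*Combined protocol and SAP*

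**What the plan says.** **Lesions per subject.** The second inclusion criterion (4.2.1) reads "Subject has 1-2 primary, non-recurrent, superficial, or nodular visible basal cell carcinoma lesion up to 1.5 cm in size", and section 3.2 also allows one or two. Section 6.5 caps the study at 30 participants, so the data may hold 30 to 60 lesions.

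**Partial response (6.3.3).** The unit is the lesion: "The number and proportion of lesions meeting the definition of partial response and confidence interval for the proportion will be calculated". Neither the interval method nor its level is given.

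**Scar scores (6.3.4, 6.3.5).** Scores are collected per area. At Visit 6 (4.10), "The subject shall assess each treatment area based on the SCAR-Q Appearance Scale prior to excision". The Manchester instruction, "The site investigator shall assess each treatment area based on the Manchester Scar Scale", appears at Visit 6 (4.10) and again at Visit 9 (4.13). SCAR-Q is also repeated at Visit 9. Least-squares means come from models fitted "using generalized linear models with lesion size included as a fixed effect" for SCAR-Q and "using generalized linear models with treatment lesion size included as a fixed effect" for Manchester. No subject term, clustered variance or visit term is named.

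**Elsewhere.** The mixed model in 6.3.1 covers change in lesion size only. The longitudinal model in 6.9 is a sensitivity analysis for missing data. Section 6.1 plans no inferential tests, and 6.3 calls any p-values for secondary endpoints descriptive.

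**The concern.** Two lesions on one person share skin, healing tendency and investigator; for SCAR-Q they also share the rater. Their outcomes are likely to resemble each other. An analysis that counts them as independent credits the study with more information than it has, and its intervals come out too narrow.

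Because no tests are planned, the intervals are the study's statement of uncertainty. Section 1.6 says the data will be used to design a pivotal study, so overstated precision could carry forward.

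A separate gap sits in the same two sections. Visit 6 scores the area after CellFX treatment, and Visit 9 scores it after excision. Sections 6.3.4 and 6.3.5 do not say whether the two visits are modelled apart.

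**Working it through.** The plan gives no precision target, so there is no figure of its own to reproduce. The check asks how far an interval that ignores pairing falls short of 95%.

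**Inputs.** From the documents: at most 30 subjects, one or two lesions each. Assumed, because the documents do not give them: k, the number of subjects with two lesions; the intraclass correlation (ICC) within a subject, 0.3, 0.5 or 0.8; the true response rate; a 95% level; and, for 6.3.3, an exact (Clopper-Pearson) interval.

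**Step 1: design effect.** With 30 + k lesions and k pairs,

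DEFF = [(30 − k) + 2k(1 + ICC)] / (30 + k) = 1 + ICC × 2k / (30 + k).

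- k = 3, ICC 0.5: 1 + 0.5 × 6/33 = 1.091; √DEFF = 1.044.
- k = 10, ICC 0.8: 1 + 0.8 × 20/40 = 1.40; √DEFF = 1.183.
- k = 30, ICC 0.8: 1 + 0.8 × 60/60 = 1.80; √DEFF = 1.342.

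**Step 2: scar means (6.3.4, 6.3.5).** To a normal approximation, the coverage of an interval that ignores pairing is 2Φ(1.96/√DEFF) − 1. For the three cases this gives 93.9%, 90.2% and 85.6%. Simulation agrees (20,000 replicates per cell, one visit, normal scores, lesion size as covariate):

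| k | ICC 0.3 | ICC 0.5 | ICC 0.8 |
|---|---|---|---|
| 2 | 94.4% | 94.2% | 94.1% |
| 3 | 94.3% | 94.1% | 93.5% |
| 4 | 93.9% | 93.7% | 93.1% |
| 6 | 94.0% | 93.1% | 92.0% |
| 10 | 93.3% | 92.1% | 90.0% |
| 30 | 91.4% | 89.1% | 85.7% |

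Subject-clustered standard errors with a t reference on 29 degrees of freedom restore coverage to about 94-95% throughout.

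**Step 3: partial response (6.3.3).** Coverage of the exact interval over 30 + k lesions, by full enumeration of 30 − k single lesions and k correlated pairs. The ICC 0 column separates the effect of pairing from binomial discreteness.

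| True rate | k | ICC 0 | ICC 0.3 | ICC 0.5 | ICC 0.8 |
|---|---|---|---|---|---|
| 0.8 | 3 | 97.3% | 96.8% | 96.6% | 96.1% |
| 0.8 | 6 | 96.6% | 95.6% | 95.0% | 94.0% |
| 0.8 | 15 | 96.2% | 94.2% | 92.8% | 90.6% |
| 0.8 | 30 | 96.6% | 93.7% | 91.6% | 88.5% |
| 0.9 | 3 | 98.6% | 98.3% | 98.2% | 97.9% |
| 0.9 | 6 | 95.4% | 94.3% | 93.5% | 92.3% |
| 0.9 | 15 | 97.9% | 96.5% | 95.4% | 93.4% |
| 0.9 | 30 | 97.2% | 94.5% | 92.5% | 89.8% |

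Over k = 1-4 the lowest coverage is 94.9% at rate 0.8, 97.3% at 0.9 and 96.8% at 0.95. At rate 0.95 the lowest over every k from 1 to 30 is 93.8% (k = 27, ICC 0.8). The dip at rate 0.9 and k = 6 is partly discreteness, since coverage is already down to 95.4% there with no correlation.

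The method matters. At rate 0.8 and k = 3, a Wilson interval goes from 95.2% (ICC 0) to 94.1% (ICC 0.5).

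**The case against.** The strongest reply is that few subjects may have two lesions. Section 1.5 says of an earlier feasibility study: "A portion of 1-2 biopsy confirmed BCC lesions were treated in the 48 Subjects enrolled. 48 NPS treated areas were evaluated". One evaluated area per subject hints at a small k. The hint is weak, because the passage does not say how many areas were treated, but it is the only one in the documents. At k = 2-4 the scar means lose one or two points of coverage at most, and an exact interval in 6.3.3 loses nothing that matters. These are also secondary, descriptive intervals in a feasibility study. All of this stands and sets the severity.

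Two stronger readings are tempting. A reader might infer that the 6.3.3 interval under-covers whenever lesions are correlated. The plan names no method there, and an exact interval is conservative enough to absorb a few pairs. It is narrower than a clustered interval, but being narrower is not the same as missing its nominal level.

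A reader might also carry the point over to the primary endpoint. Section 6.2 does not settle this either way: its references to patients and subjects describe the analysis populations, the proportion has no stated unit, and Table 1 defines clearance on the target lesion. The text supports neither a claim that the primary interval ignores clustering nor a claim that it is safely per subject.

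**Conclusion.** The omission is real: nothing in 6.3.3, 6.3.4 or 6.3.5, or elsewhere in the plan, allows for two lesions from one subject in these analyses. Given positive within-subject correlation, the scar-mean intervals are too narrow, slightly if few subjects have two lesions and appreciably if most do. For 6.3.3, under an exact interval, material under-coverage needs many two-lesion subjects and a response rate around 0.8-0.9. The sizes rest on the assumed k, ICC, rate and level. The direction rests only on positive correlation and at least one subject with two lesions.

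Severity is minor. No test, decision rule or sample size depends on these intervals. The handling of Visits 6 and 9 and the unit in 6.2 are separate clarifications and do not raise the severity.

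**What to change.** - **6.3.4 and 6.3.5:** use subject-clustered standard errors with a small-sample correction (t with the number of subjects minus 1 degrees of freedom). Fit Visit 6 and Visit 9 separately, or include a visit term. A subject random effect is less attractive, because with two to four pairs its variance would be poorly estimated.
- **6.3.3:** keep the lesion-level proportion but base its interval on a subject-clustered method, or use an exact interval on one prespecified lesion per subject. Keep the ordinary exact interval if no subject has two lesions. State the method and the level.
- **6.2 (clarification):** say whether the unit is the subject or the lesion. If it is the subject, say how one with one cleared and one uncleared lesion counts.

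The cost is SAP wording, minor programming and somewhat wider intervals. Single-visit scar-mean intervals widen by about 1-8% at k = 2-4, 5-12% at k = 6, 7-18% at k = 10 and 16-37% at k = 30. For 6.3.3 at true rate 0.8, a clustered interval moves the mean width from 28.7 to 29.6 percentage points (k = 3, ICC 0.5) and from 21.1 to 28.3 (k = 30, ICC 0.8). At rate 0.95 it goes from 17.5 to 20.3 points (k = 3, ICC 0.5) with no real gain in coverage, which favours the simpler one-lesion option if very high response is expected.
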